11. PHARMACODYNAMIC ANALYSES

11.1. Blood Eosinophils

11.1.1. Population of Interest

Blood eosinophil analyses will be based on the Pharmacodynamic population.

11.1.2. Endpoint / Variables

Absolute and ratio to baseline blood eosinophil counts at each visit. For blood eosinophils, baseline will be defined as the latest blood eosinophil value measured by the central laboratory prior to the first dose of 205203 study treatment.

11.1.3. Summary Measure

The blood eosinophil ratio to baseline.

11.1.4. Strategy for Intercurrent (Post-Randomization) Events

For subjects withdrawing prematurely from study treatment, only the endpoint values up to and including 28 days after the last dose of study treatment will be included in the analysis ('while on treatment' estimand).

11.1.5. Statistical Analyses / Methods

- Blood eosinophil counts will be \log_e -transformed prior to analysis. The log transformation for values of 0 GI/L will be based on a value of 0.005 GI/L
- Absolute and ratio to baseline blood eosinophil counts will be summarised by previous treatment group from study 200622 and visit. Descriptive statistics will

include: Minimum, maximum, median, geometric mean on the original scale and standard deviation on \log_e -transformed data.

- Geometric mean blood eosinophil counts will be plotted by previous treatment group, immunogenicity status and visit.
- Only results from the central laboratory will be included in the summary, however all data will be listed.

Details of the planned displays are provided in [Appendix 8: List of Data Displays](#) and will be based on GSK Data Standards and statistical principles.

13. APPENDICES

13.1. Appendix 1: Schedule of Activities

13.1.1. Protocol Defined Schedule of Events

Procedure Study Visit	Screening/Baseline 1	20-Week Treatment Period					WD (4 weeks post-last dose) ± 1 wk	Study Visit 7 Additional follow-up (12 weeks post-last dose ± 1 wk)	Flare	Notes
		2	3	4	5	6				
Study Weeks	0	4 ± 1 wk	8 ± 1 wk	12 ± 1 wk	16 ± 1 wk	20 ± 1 wk				
Informed consent	X									
Inclusion and exclusion criteria	X									
Demography	X									
Full physical examination including height and weight	X									
Past and current medical conditions	X									
Urine pregnancy test (WOCBP only) – serum test if locally required	X	X	X	X	X	X	X	X		Test is required for WOCBP on study treatment until the last follow-up.
Clinical safety laboratory assessments (include liver chemistries)	1	2	2	2	2	1	1		2	1: Hematology, chemistry, aldolase, troponin, urinalysis 2: Hematology, chemistry, aldolase, troponin
PK	X					X	X	X		
Immunogenicity (Anti-drug antibody)	X					X	X	X		
12-lead ECG	X					X	X			

Procedure	Screening/Baseline	20-Week Treatment Period					WD (4 weeks post-last dose) ± 1 wk	Study Visit 7 Additional follow-up (12 weeks post-last dose ± 1 wk)	Flare	Notes
		2	3	4	5	6				
Study Visit	1									
Study Weeks	0	4 ± 1 wk	8 ± 1 wk	12 ± 1 wk	16 ± 1 wk	20 ± 1 wk				
Vital signs	X	X	X	X	X	X	X		X	
HES Core Assessments/HES flare details	X	X	X	X	X	X	X		X	
Study treatment	X	X	X	X	X					
AE review	X	X	X	X	X	X	X	X	X	
SAE review	X	X	X	X	X	X	X	X	X	
Concomitant medication review	X	X	X	X	X	X	X	X	X	

wk: week

- The baseline visit is the exit visit (32 weeks after randomization) for Study 200622. Assessments that are captured as part of the exit visit for Study 200622 do not have to be repeated. Information will be transferred accordingly.
- Biological sample collection (for clinical safety laboratory, PK, and immunogenicity) is done prior to administration of study treatment on dosing visits (Visits 1 2, 3, 4, 5) as specified in the SoA.
- WD: Prematurely discontinuation of mepolizumab (~4 weeks after the last dose of mepolizumab).
- Visit 7 - Additional follow-up is required 12 weeks after the last dose of mepolizumab for participants who do not continue with mepolizumab via MHE104317/MHE112562 at that time.
- Participants who prematurely discontinue study treatment will attend 4-weekly study visits (e.g., Visit 2, 3, 4, 5) to complete all assessments/procedures as noted in the SoA except for administration of study treatment and pre-dose pregnancy test for women of childbearing potential (WOCBP). For additional assessments at 4 weeks and 12 weeks after the last dose of

- mepolizumab (duplicate assessments in 4-weekly study visits and 4 weeks/12 weeks post-last dose assessments are completed only once), refer to 'WD' and 'Visit 7- Additional follow-up'.
- Any changes in the timing or addition of time points for any planned study assessments must be documented and approved by the relevant study team member and then archived in the sponsor and site study files, but will not constitute a protocol amendment. The IRB/IEC will be informed of any safety issues that require alteration of the safety monitoring scheme or amendment of the ICF.

13.2. Appendix 2: Study Phases and Treatment Emergent Adverse Events

Assessments and events will be classified according to the time of occurrence relative to the first dose of open-label mepolizumab.

Time	Subjects completing the study (Week 20 visit)	Subjects not completing the study (Predicted Week 20 visit date = Date of first dose + 140 days)
Total observed time	Week 20 visit date – date of first dose + 1 day	Study withdrawal date – date of first dose + 1 day
Time on treatment (days)	Minimum(Week 20 visit date, Date of last dose + 28 days) - Date of first dose + 1 day	Minimum(Study withdrawal date, Date of last dose + 28 days) - Date of first dose + 1 day
Time off treatment (days)	Week 20 visit date – Minimum(Week 20 visit date, Date of last dose + 28 days)	Study withdrawal date – Minimum(Study withdrawal date, Date of last dose + 28 days)
Missing time	0	Predicted Week 20 visit date – Study withdrawal date

13.2.1. Treatment Phases for Adverse Events

Treatment State	Definition
Pre-Treatment	
 AE start date < Date of first dose of open-label mepolizumab or if AE onset date/time is available AE start date/time < Date/time of first dose of open-label mepolizumab
On-Treatment	
 Date of first dose of open-label mepolizumab ≤ AE start date ≤ Date of last dose of open-label mepolizumab + 28 days or if AE onset date/time is available Date/time of first dose of open-label mepolizumab ≤ AE start date/time ≤ Date/time of last dose of open-label mepolizumab + 28 days Any adverse event with missing start date will be assumed to be “On-Treatment”. Any adverse event with partial start date will be assumed to be “On-Treatment” unless there is evidence to the contrary (e.g. month/year of onset is present and is earlier than the month/year of the first dose of study treatment).
Post-Treatment	
 AE start date > Date of last dose of open-label mepolizumab + 28 days or if AE onset date/time is available AE start date/time > Date/time of last dose of open-label mepolizumab + 28 days

13.2.2. Study Phases for Concomitant Medication

Study Phase	Definition
Prior	If medication end date is not missing and is before the date of first dose of study treatment
Concomitant	Any medication that is not a prior

NOTES:

- Please refer to Section [13.5.2](#) for handling of missing and partial dates for concomitant medications.

13.3. Appendix 3: Data Display Standards & Handling Conventions

13.3.1. Reporting Process

Software	

 The currently supported versions of SAS software will be used. 	
Reporting Area	
HARP Server	: uk1salx00175
HARP Area	: sb240563/mid205203
Analysis Datasets	

 Analysis datasets will be created according to CDISC standards. For creation of ADaM datasets (ADCM/ADAE), the same version of dictionary datasets will be implemented for conversion from SI to SDTM. 	
Generation of RTF Files	

 RTF files will be generated for the final reporting effort. 	

13.3.2. Reporting Standards

General	

 All data displays (Tables, Figures & Listings) will use the term “Subject” rather than “Participant” which reflects CDISC and GSK Data Display Standards terminology. The current GSK Integrated Data Standards Library (IDSL) will be applied for reporting, unless otherwise stated (IDSL Standards Location: https://spope.gsk.com/sites/IDSLLibrary/SitePages/Home.aspx): 
 4.03 to 4.23: General Principles 5.01 to 5.08: Principles Related to Data Listings 6.01 to 6.11: Principles Related to Summary Tables 7.01 to 7.13: Principles Related to Graphics Do not include subject level listings in the main body of the GSK Clinical Study Report. All subject level listings should be located in the modular appendices as ICH or non-ICH listings 	
Formats	

 GSK IDSL Statistical Principles (5.03 & 6.06.3) for decimal places (DPs) will be adopted for reporting of data based on the raw data collected but may be adjusted to a clinically interpretable number of DPs. 	
Planned and Actual Time	

 Reporting for tables, figures and formal statistical analyses: 
 Planned time relative to dosing will be used in figures, summaries, statistical analyses and calculation of any derived parameters, unless otherwise stated. The impact of any major deviation from the planned assessment times and/or scheduled visit days on the analyses and interpretation of the results will be assessed as appropriate. Reporting for Data Listings: 
 Planned and actual time relative to study drug dosing will be shown in listings (Refer to IDSL Statistical Principle 5.05.1). 	

 • Unscheduled or unplanned readings will be presented within the subject’s listings. • Visits outside the protocol defined time-windows (i.e. recorded as protocol deviations) will be included in listings, summaries and statistical analyses. 	
Unscheduled Visits	

 • HES flare data collected at unscheduled visits will be included in the derivation of the rate of HES flares • For summaries by visit, data recorded at an unscheduled visit will be re-assigned in the ADaM data sets to the closest nominal visit at which collection of data was scheduled, unless information already exists at that visit. Unscheduled data re-assigned to a scheduled visit will be included in analyses, summary tables and figures by scheduled visit. Unscheduled data that is not re-assigned to a scheduled visit will not be included in analyses, summary tables or figures by scheduled visit. Unscheduled data that is not re-assigned to a scheduled visit will be considered in the derivation of baseline and highest/worst case post baseline result for relevant summary tables. • Data recorded at unscheduled visits will be included in the assessment of maximum or worst case post-baseline for relevant endpoints. • All unscheduled visits will be included in listings. 	
Early Withdrawal Visits	

 • Data recorded at the early withdrawal visit will be re-assigned in the ADaM data sets to the next scheduled visit, unless information already exists at that visit. Early withdrawal data re-assigned to a scheduled visit will be included in analyses, summary tables and figures by scheduled visit. Early withdrawal visit data that is not re-assigned to a scheduled visit will not be included in analyses, summary tables or figures by scheduled visit. • Data recorded at early withdrawal visits will be included in the assessment of maximum or worst case post-baseline for relevant endpoints. • Data from all early withdrawal visits will be included in listings. 	
Descriptive Summary Statistics	
Continuous Data	Refer to IDSL Statistical Principle 6.06.1
Categorical Data	N, n, frequency, %
Graphical Displays	

 • Refer to IDSL Statistical Principals 7.01 to 7.13. 	

13.3.3. Reporting Standards for Pharmacokinetic Data

Pharmacokinetic Concentration Data	
Descriptive Summary Statistics, Graphical Displays and Listings	Refer to IDSL PK Display Standards. Refer to IDSL Statistical Principle 6.06.1. Note: BLQ concentration values will be imputed as per GUI_51487 for descriptive summary statistics only.

13.4. Appendix 4: Derived and Transformed Data

13.4.1. General

Multiple Measurements at One Analysis Time Point

 • May arise when unscheduled visits are re-assigned to a nominal visit (see Section 13.1.1). If there is data at the nominal visit, the nominal visit data will be used in the summary tables and figures. All assessments will be listed. • Participants having both High and Low values for Normal Ranges at any post-baseline visit for safety parameters will be counted in both the High and Low categories of “Any visit post-baseline” row of related summary tables. This will also be applicable to relevant Potential Clinical Importance summary tables. • If multiple ECG assessments are performed at a single time point, for each ECG parameter, the mean of the parameter values from replicate ECGs will be used in the derivation of any summary statistics for that ECG parameter. All data will be listed.
Study Day

 • Calculated as the number of days from the date of the first dose of open-label mepolizumab: 
 • Ref Date = Missing → Study Day = Missing • Ref Date < First date of open-label mepolizumab → Study Day = Ref Date – First date of open-label mepolizumab • Ref Date ≥ First date of open-label mepolizumab → Study Day = Ref Date – (First date of open-label mepolizumab) + 1

13.4.2. Change from Baseline Definitions

Definition	Reporting Details
Change from Baseline	= Post-Dose Visit Value – Baseline
% Change from Baseline	= 100 x [(Post-Dose Visit Value – Baseline) / Baseline]
Ratio to Baseline	= Visit Value / Baseline

13.4.3. Study Population

Age

 • GSK standard IDSL algorithms will be used for calculating age where birth day and month will be imputed ‘30th June’. • Birth date will be presented in listings as ‘YYYY’. • Age will be calculated relative to the date of the screening visit (Visit 1).
Body Mass Index (BMI)

 • Calculated as Weight (kg) / [Height (m)²]
Extent of Exposure

 • Number of days of exposure to open-label mepolizumab will be calculated based on the

formula:

$$\text{Duration of Exposure in Days} = \text{Date of Last Dose of Open-Label Mepolizumab} - \text{Date of First Dose of Open-Label Mepolizumab} + 29.$$

13.4.4. Efficacy

HES Flare

Definition of HES Flare

A HES flare is defined as an HES-related clinical manifestation based on a physician-documented change in clinical signs or symptoms (worsening symptoms and/or elevated blood eosinophil level) resulting in the need for either of the following:

- An increase from the most recent dose in the maintenance OCS dose (prednisone/prednisolone equivalent) by at least 10mg/day for 5 days
- An increase in or addition of any cytotoxic and/or immunosuppressive HES therapy from/to the most recent dose of HES therapy.

To be considered as an HES flare, the most recent dose of HES therapy must not have changed for at least 4 weeks. This ensures that failed reductions in HES therapy are not misclassified as an HES flare.

The start date for an HES flare will be defined as the date of therapy escalation confirmed by the investigator attributable to an HES-related clinical manifestation.

When a subject experiences an HES flare, the investigator will monitor the change in disease control per routine medical care (e.g., follow-up call) and record the resolution of the flare including the end date. Investigators are encouraged, as medically appropriate, to return the subject’s treatment regimen to the baseline (Visit 2) after the flare has resolved.

In the event of disease worsening for which the investigator suspects an HES flare between scheduled clinic visits, when possible, the subject will return to the clinic to have the unscheduled ‘Flare’ visit assessment completed as described in the SoA. When attending the clinic visit at the time of a suspected HES flare is not possible, the investigator should make every effort to evaluate the subject via telephone and complete the HES Core Assessments (Section 9.1.2). If an escalation of therapy is initiated by a non-study physician, the investigator should confirm that the escalation in therapy is attributable to an HES-related clinical manifestation.

Investigators will be required to record details pertaining to the HES flare event in the CRF from Visit 1 until 20 weeks after the first dose of mepolizumab. This should include details regarding the clinical symptoms resulting in the flare with detail of the required intervention(s), e.g., OCS dose increase, or addition or escalation of immunosuppressive or cytotoxic therapy. In addition, all other relevant clinical, laboratory or other diagnostic investigations required to confirm the flare must be captured in the CRF.

The definition of HES flare for this study (205203) is different from that for the preceding, randomized Study 200622. This difference in definitions is due to the requirement during Study 200622 to avoid decreases in background HES therapy that may confound a blinded subject’s clinical status as well as the requirement in Study 200622 to blind blood eosinophil levels. In Study 205203, all participants will receive mepolizumab and investigators will be unblinded to blood eosinophil levels starting 4 weeks after the first dose (Visit 2) so that they may adjust background HES therapy as per SoC.

Rate of HES Flares

- For subjects completing the study, the rate of HES flares will be calculated as

$$\frac{365.25 \times \text{Number of observed HES flares}}{\text{Date of Week 20 (Visit 6)} - \text{Date of first dose of mepolizumab} + 1}$$
- For subjects withdrawing prematurely from the study, the rate of HES flares will be calculated as

$$\frac{365.25 \times \text{Number of observed HES flares}}{\text{Date of study withdrawal} - \text{Date of first dose of mepolizumab} + 1}$$

The number of HES flares is the number of unique starting dates for HES flares. To be considered as a separate episode of HES flare, the start date of an HES flare must be at least 14 days apart from the resolution date of the preceding HES flare.

Oral Prednisone Equivalent Daily Dose

- For each subject, oral prednisone equivalent daily dose (mg) on each day of the study will be identified from the concomitant medications page
- Partial start and end dates for concomitant medications will be handled as described in Section 13.5.2.
- Corticosteroids will be identified from the list of coded concomitant medications for the study, by merging with the GSK respiratory medication class (RMC) reference data set by component code. This reference data is created by dictionary specialists who identify a list of component terms for corticosteroids, which then undergo clinical review to ensure the correct classification is assigned.
- Only corticosteroids recorded with route = “PO” will be considered as oral corticosteroids.
- Subjects not receiving OCS therapy on any day of the study will be assigned a prednisone equivalent daily dose of 0 mg for that day.
- The corticosteroid conversion factors in the table below will be used to scale each corticosteroid dose to a prednisone equivalent dose.

Medication Name	Scaling Factor
Betamethasone	8.33
Budesonide ¹	0
Cortisone	0.2

Dexamethasone	6.67
Deflazacort	0.83
Hydrocortisone	0.25
Methylprednisone	1.25
Meprednisone	1.25
Prednisone	1
Prednisolone	1
Prednisone acetate	1
Triamcinolone	1.25

¹Budesonide has negligible systemic exposure and will be classed as “Other HES therapy” rather than oral corticosteroid therapy.

- Where the frequency of the recorded corticosteroid dose is not once daily, the following calculations will be used to determine the daily dose.

Medication Frequency	Daily Dose Equivalent
BID	2 x dose
TID	3 x dose
QID	4 x dose
QOD	dose / 2
2XWK	(2 x dose) / 7
3XWK	(3 x dose) / 7
4XWK	(4 x dose) / 7
5XWK	(5 x dose) / 7

Mean Daily OCS Dose
Change in the mean daily OCS dose from Weeks 0-4 to Weeks 16-20

 The mean daily OCS dose for weeks 0-4 will be calculated as $\frac{\textit{Sum of daily OCS dose for weeks 0 - 4}}{28}$ The mean daily OCS dose for weeks 16-20 will be calculated as $\frac{\textit{Sum of daily OCS dose for weeks 16 - 20}}{28}$ The change in the mean daily OCS dose from Weeks 0-4 to Weeks 16-20 will be the difference of mean daily OCS dose for weeks 16-20 minus mean daily OCS dose for weeks 0-4

13.4.5. Safety

Adverse Events
Drug Related AEs
AEs with relationship marked 'YES' or relationship missing.
AEs Leading to Permanent Discontinuation from Study Treatment or Withdrawal from the Study
AEs with action marked "Study treatment withdrawn" or withdrawn from study status marked "YES", or a response to either of these questions is missing.
AE Duration (Days)

 AE end date – AE start date + 1 Missing if AE start date or end date is missing.
AEs of Special Interest

 See Section 7.2.

13.5. Appendix 5: Reporting Standards for Missing Data

13.5.1. Premature Withdrawals

Element	Reporting Detail
General	
 • A subject will be considered to have completed study treatment if they receive study treatment at week 16 (Visit 5). • Subjects who discontinue study treatment or withdraw early will not be replaced in the study.

13.5.2. Handling of Missing and Partial Dates

Element	Reporting Detail
General	
 • Partial dates will be displayed as captured in subject listing displays.
Adverse Events and HES Flare	
 • Any partial dates for adverse events or HES flare will be raised to data management. If the full dated cannot be ascertained, the following assumptions will be made: 
 ○ If the partial date is a start date, a '01' will be used for the day and 'Jan' will be used for the month. ○ However, if this imputation results in a date prior to the first dose of open-label mepolizumab and the event could possibly have occurred during open-label mepolizumab treatment from the partial information, then the date of the first dose of mepolizumab will be assumed to be the start date. ○ The event will then be considered to start on-treatment (worst case). ○ If the partial date is a stop date, a '28/29/30/31' will be used for the day (dependent on the month and year) and 'Dec' will be used for the month. • Completely missing start or end dates will remain missing, with no imputation applied. Consequently, time to onset and duration of such events will be missing. Such events will be considered to have started after the first dose of open-label mepolizumab. • The recorded partial date will be displayed in listings.
Concomitant Medications	
 • Partial dates for any concomitant medications recorded in the CRF will be imputed using the following convention: 
 • If the partial date is a start date, a '01' will be used for the day and 'Jan' will be used for the month • If the partial date is a stop date, a '28/29/30/31' will be used for the day (dependent on the month and year) and 'Dec' will be used for the month. • The recorded partial date will be displayed in listings.

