7.2. Adverse Events of Special Interest Analyses

- Adverse events of special interest (AESIs) reported by the investigator as systemic reactions (further categorised by the investigator as either allergic [type I hypersensitivity] or other systemic reactions and assessed against Sampson criteria for anaphylaxis) are collected via targeted eCRF within the study. Local injection site reactions are also collected via targeted eCRF within the study.
- AESIs of opportunistic infections, malignancies, serious cardiac vascular and thromboembolic (CVT) events and serious ischemic events will be identified from a list of relevant preferred terms maintained within a project level reference dataset created based on the MedDRA dictionary available at the time of database freeze for this study. Further details of how relevant preferred terms are identified are given in the Program Safety Analysis Plan (PSAP).
- Separate summary tables showing the number and percent of participants with each type of AESI, broken down by preferred term will be created.
- For each type of AESI a profile summary table will be produced containing information including, but not be limited to, the number of occurrences of the event, event characteristics, time to onset, intensity, outcome and action taken.
- Separate listings of AESIs identified by the investigator as anaphylaxis, allergic (type I hypersensitivity), other systemic reactions and local injection site reactions will be

produced, as well as listings of opportunistic infections, malignancies, serious CVT events and serious ischemic events.

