9. EFFICACY ANALYSES

9.1. Exploratory Efficacy Analyses

9.1.1. Rate of HES Flares

9.1.1.1. Endpoint / Variables

Definition of HES Flare

A HES flare is defined as an HES-related clinical manifestation based on a physician-documented change in clinical signs or symptoms (worsening symptoms and/or elevated blood eosinophil level) resulting in the need for either of the following:

- An increase from the most recent dose in the maintenance OCS dose (prednisone/prednisolone equivalent) by at least 10mg/day for 5 days
- An increase in or addition of any cytotoxic and/or immunosuppressive HES therapy from/to the most recent dose of HES therapy.

To be considered as an HES flare, the most recent dose of HES therapy must not have changed for at least 4 weeks. This ensures that failed reductions in HES therapy are not misclassified as an HES flare.

The definition of HES flare for this study (205203) is different from that for the preceding, randomized Study 200622. This difference in definitions is due to the requirement during Study 200622 to avoid decreases in background HES therapy that may confound a blinded subject's clinical status as well as the requirement during Study 200622 to blind blood eosinophil levels. In Study 205203, all participants will receive mepolizumab and investigators will be unblinded to blood eosinophil levels starting 4 weeks after the first dose (Visit 2) so that they may adjust background HES therapy as per standard of care (SoC).

Derivation of Endpoint

The rate of HES flares will be calculated for each subject as the number of observed HES flares divided by the time (expressed in years) between the first dose of study treatment in Study 205203 and either the Week 20 visit date if available, or otherwise the study withdrawal date (see Section [13.4.4](#)).

The rate of HES flares will also be calculated separately using data from Study 200622 only, for those subjects continuing into Study 205203.

The number of observed HES flares will be calculated for each subject as the number of unique starting dates for HES flares. To be considered as a separate episode of HES flare, the onset date of an HES flare must be at least 14 days apart from the resolution date of the preceding HES flare.

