13.8.5. Safety Tables

No.	Population	IDSL / Example Shell	Title	Programming Notes	Deliverable
Adverse Events					
2.1.	Safety	AE1	Summary of All On-Treatment Adverse Events by System Organ Class and Preferred Term		SAC
2.2.	Safety	AE1	Summary of All Post-Treatment Adverse Events by System Organ Class and Preferred Term		SAC
2.3.	Safety	AE3	Summary of Common ($\geq 3\%$ Incidence) On-Treatment Adverse Events by Overall Frequency		SAC
2.4.	Safety	AE15	Summary of Common ($\geq 3\%$ Incidence) On-Treatment Non-Serious Adverse Events by System Organ Class and Preferred Term (Number of Subjects and Occurrences)		SAC
2.5.	Safety	AE5A	Summary of All On-Treatment Adverse Events by Maximum Intensity by System Organ Class and Preferred Term		SAC
2.6.	Safety	AE1	Summary of All Drug-Related Adverse Events by System Organ Class and Preferred Term		SAC
2.7.	Safety	AE5A	Summary of All Drug-Related Adverse Events by Maximum Intensity by System Organ Class and Preferred Term		SAC
2.8.	Safety	AE1	Summary of Non-Serious Drug-Related Adverse Events by System Organ Class and Preferred Term		SAC
2.9.	Safety	AE1	Summary of On-Treatment Adverse Events by Highest Post-Baseline Binding Antibody Result	Add in row with n in each binding antibody result category.	SAC
2.10.	Safety	AE3	Summary of All Adverse Events Leading to Permanent Discontinuation from Study Treatment by Overall Frequency		SAC

CONFIDENTIAL

205203

No.	Population	IDSL / Example Shell	Title	Programming Notes	Deliverable
Adverse Events					
2.11.	Safety	AE3	Summary of All Adverse Events Leading to Withdrawal from the Study by Overall Frequency		SAC
2.12.	Safety	AE1	Summary of Adverse Events Reported on the Day of Dosing by System Organ Class and Preferred Term		SAC
2.13.	Safety	AE7	Listing of Subject Numbers for Individual On-Treatment Adverse Events		SAC
2.14.	Safety	AE7	Listing of Subject Numbers for Individual Post-Treatment Adverse Events		SAC
2.15.	Safety	AE2	Listing of Relationship of Adverse Event, System Organ Classes, Preferred Terms and Verbatim Text		SAC
Adverse Event Overview					
2.16.	Safety	SAFE_T1	Adverse Event Overview		SAC
Serious Adverse Events					
2.17.	Safety	AE3	Summary of Fatal Serious Adverse Events by Overall Frequency		SAC
2.18.	Safety	AE3	Summary of Drug-Related Fatal Serious Adverse Events by Overall Frequency		SAC
2.19.	Safety	AE3	Summary of Non-Fatal Serious Adverse Events by Overall Frequency		SAC
2.20.	Safety	AE3	Summary of All Serious Adverse Events by Overall Frequency		SAC

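### Imputed partial AE and flare dates, sound for assigning treatment phase, also enter AE duration, time to onset and the 14-day flare-gap rule, which biases timing and can merge separate flares

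*SAP*

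**What the plan says.** The row of SAP 13.5.2 on adverse events and HES flares works in four steps.

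- **Query first.** "Any partial dates for adverse events or HES flare will be raised to data management". Imputation applies only to what stays unresolved.
- **Start dates.** The missing day becomes the 1st and the missing month January. There is one exception: "if this imputation results in a date prior to the first dose of open-label mepolizumab and the event could possibly have occurred" on treatment, "then the date of the first dose of mepolizumab will be assumed to be the start date". The SAP labels the resulting on-treatment status a worst case.
- **Stop dates.** The missing day becomes the last of the month and the missing month December.
- **Completely missing dates.** These stay missing. "Consequently, time to onset and duration of such events will be missing".

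The dates are then used elsewhere:

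- SAP 13.4.5 defines AE duration as end minus start plus 1, blank only if a date is missing.
- SAP 7.2 promises a profile table for each type of event of special interest, covering "event characteristics, time to onset, intensity, outcome and action taken".
- SAP 13.8.5 lists Table 2.12, "Summary of Adverse Events Reported on the Day of Dosing by System Organ Class and Preferred Term". Listing 17 in 13.8.12 covers the same events.
- SAP 9.1.1.1, repeated in 13.4.4, counts a flare as separate only if "the onset date of an HES flare must be at least 14 days apart from the resolution date of the preceding HES flare".

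SAP 13.5.2 also says that listings show the partial date as recorded.

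**The concern.** Earliest start and latest stop are the right choices for one question: could this event have been on treatment? They are poor estimates of when an event began or how long it lasted, and the SAP does not confine them to the first use. The result is uneven. An event with no date at all has no onset or duration, while an event known only to a month or a year is given an exact value for each that nobody recorded.

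Adverse events are the primary endpoint, and timing relative to dosing and duration are among the features used to describe injection-related events. For flares, a later resolution and an earlier next onset both shorten the gap between episodes. Under the 14-day rule, imputation can therefore only merge flares. That lowers the flare rate, and SAP 9.1.1.4 plans no sensitivity analysis for it.

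**Working it through.** The documents give no figure to reproduce and no count of partial dates, so all results are per partly dated event.

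**Inputs from the documents:** doses on days 0, 28, 56, 84 and 112; onset on any of days 0 to 140 (141 days); the imputation rules of 13.5.2; the duration formula of 13.4.5; the 14-day rule of 9.1.1.1.

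**Assumptions:** first dose equally likely on each of 365 days; onset uniform over the 141 days; a non-leap year with seven 31-day months, four 30-day months and one 28-day month. This gives 365 × 141 = 51,465 equally likely pairs of first dose and onset.

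**1. Start with the day missing**
- Moved onto the first dose: onset is in the same month as the first dose, and the first dose is after the 1st. A month of n days gives n(n−1)/2 pairs: 7 × 465 + 4 × 435 + 378 = 5,373, or 10.4%.
- First dose already on the 1st: 365 further pairs. Total on the first-dose date: 5,738 / 51,465 = 11.1%.
- A later dose on the 1st of the onset month: 3 × 365 for days 28, 56 and 84, plus 7 × 29 + 4 × 29 + 28 = 347 for day 112 (cut off at day 140), which is 1,442.
- On any dosing day: (5,738 + 1,442) / 51,465 = 14.0%. Truly on a dosing day: 5/141 = 3.5%. The ratio is about 4.

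**2. Start with only the year known**
- Onset in the same calendar year as the first dose: (51,465 − 140 × 141/2) / 51,465 = 41,595 / 51,465 = 80.8%. Each of these is dated to the first dose.

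**3. Duration of a true 4-day AE, day missing**
- The imputed start is on average 13.6 days early (by enumeration).
- The imputed stop is on average 5,373/365 = 14.7 days late.

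| Partial date | Mean duration (days) |
|---|---|
| Start only | 4 + 13.6 = 17.6 |
| Stop only | 4 + 14.7 = 18.7 |
| Both | 4 + 13.6 + 14.7 = 32.3 |

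**4. Flare merging, day of the preceding resolution missing**
- Imputed gap = true gap − days left in the month of resolution. The flares merge if this is below 14.
- True gap 28: merges if more than 14 days are left, i.e. (7 × 16 + 4 × 15 + 13) / 365 = 185/365 = 51%.
- True gap 42: merges if more than 28 days are left, i.e. (7 × 2 + 4 × 1 + 0) / 365 = 18/365 = 5%.

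| True gap (days) | Merged, resolution day missing | Merged, next start day also missing |
|---|---|---|
| 14 | 97% | 100% |
| 21 | 74% | 100% |
| 28 | 51% | 100% |
| 35 | 28% | 85% |
| 42 | 5% | 62% |
| 56 | 0% | 16% |

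- Effect on one subject with two flares over 141 days: 365.25 × 2/141 = 5.18 per year becomes 365.25/141 = 2.59.

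**5. The opposite direction for flares**
- Suppose a flare truly starts 1 to 28 days before the first dose and its day is missing. It is moved onto the first dose if both fall in the same month: (7 × 462 + 4 × 434 + 378) / (365 × 28) = 5,348 / 10,220 = 52%.

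**The case against.** The strongest reply is that few events will be affected and that safeguards come first. Partial dates are queried before any imputation. Dosing is supervised at the site, and participants are monitored for an hour after each of the first three administrations (Protocol 7.1, 7.5). Systemic and injection-site reactions are classified by the investigator on targeted forms (SAP 7.2), so an imputed date cannot turn an AE into a reaction. A flare starts on the date of therapy escalation and is defined by day-level criteria, so partial flare starts should be uncommon. Therapy must also have been unchanged for 4 weeks. Where a regimen is changed back after resolution, that makes gaps of 28 days or more the relevant ones. The study is descriptive and the flare rate exploratory. All of this stands, and it limits how often the problem arises. It does not justify the values reported when it does, and raw dates in listings do not correct the summary tables.

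A reader might infer more than the documents support:

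- *That every partly dated event is tied to the first dose.* With the day missing it is about 10–11%. Only year-only starts reach 81%, and a partial stop alone moves no start.
- *That short events will typically appear as month-long dosing-day reactions.* Replacement by the first-dose date itself shortens a same-month interval. For a 3-day event with both days missing, replacement together with a duration of 28 days or more occurs in about 3% of cases.
- *That flare counts can only fall.* This is true of the gap rule. But replacement by the first-dose date can bring a pre-dose flare into the count, although recording from Visit 1 should make that rare.
- *That the SAP says imputed dates feed Table 2.12.* It does not. It gives no rule either way, and the display shells are not in the document.

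**Conclusion.** The rule is wrong as written, and the point is minor. By the SAP's own definitions, imputed partial dates pass into AE duration, time to onset for events of special interest and the 14-day flare gap. Their entry into Table 2.12 and Listing 17 is not excluded, but this is an inference from silence.

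Per affected event, the distortion is a roughly four-fold excess of dosing-day starts, a 4-day AE lengthened to between about 18 and 32 days, and an even chance of merging two flares 28 days apart when the resolution day is missing. These sizes rest on uniform onset and on exactly the stated part of the date being missing. The total effect depends on how many dates stay partial after query, which the documents do not give. It concerns timing, duration and flare count. On-treatment AE incidence and the classification of reactions do not change.

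**What to change.** In SAP 13.5.2, add that:

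1. Imputed AE and flare dates are used only to assign pre-, on- or post-treatment phase.
2. Time to onset is missing if the start is partial, and duration is missing if either date is partial, as already happens for completely missing dates.
3. An event counts in Table 2.12 and Listing 17 only if its recorded full date is a dosing date.
4. Two flares are merged under the 14-day rule only when the recorded dates show a gap under 14 days. Otherwise they count as separate.

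The cost is a few sentences and an imputation-flag check in the programs. A few more onset and duration values will be missing in the profile tables for events of special interest. Item 4 may leave an occasional true single episode counted twice, which errs against the drug. Phase assignment is unchanged, so a pre-dose flare can still be placed on treatment as the SAP's stated worst case.
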